**Table 1 Apalutamide Dose Levels**

Dose Level	Total Daily Dose	Number of 60-mg Tablets (QD)
0	240 mg	4
-1	180 mg	3
-2	120 mg	2

Doses reduced for study treatment-related toxicities should generally not be re-escalated, however, re-escalation back to the previous dose level may be permitted in consultation with the Sponsor (or designee).

#### 5.4 STUDY DRUG ACCOUNTABILITY

The Sponsor (or designee) will ship study drug to the investigational sites. The initial study drug shipment will be shipped after all required regulatory documentation has been received by the Sponsor and a Clinical Trial Agreement fully executed. Subsequent study drug shipments will be made according to an automated resupply algorithm managed by the IVRS.

The study drug will only be dispensed to patients who meet the eligibility criteria and are randomized to a treatment arm in the trial. An accurate and current accounting of the dispensing and return of study drug for each patient will be maintained on an ongoing basis by the Investigator or his/her designated personnel. The number of study drug dispensed and returned by the patient will be recorded on the Investigational Product Accountability Log. The study monitor will verify these documents throughout the course of the study.

At the end of the study, the Sponsor will provide instructions as to the disposition of any unused study drug. If destruction at the site is authorized, the Investigator must ensure that all investigational product is destroyed in compliance with the applicable environmental regulations, institutional policy, and any other special instructions provided by the Sponsor. Drug destruction must be adequately documented.

## 5.5 MEASURES OF TREATMENT COMPLIANCE

At each clinic visit, patients will be asked to return any remaining study drug from the previous dosing cycle as well as all used and unused study drug containers.

The overall treatment compliance will be defined as the total dose in mg taken during the study divided by the expected total dose in mg. Patients completing their last cycle on capsules should continue with a maximum of 8 capsules per day and patients on tablets should have a maximum of 4 tablets per day.

Capsules or tablets that are not returned will be considered to have been taken, unless otherwise specified in the case report form (CRF).

## 6. CONCURRENT MEDICATIONS

All patients should be maintained on the same medications throughout the entire study period, as medically feasible, with minimum introduction of new chronic therapies. Every medication or treatment taken by the patient during the trial and the reason for its administration must be recorded on the CRF. Standard medical treatment as applicable is allowed except for treatments noted in the eligibility criteria and/or listed in the prohibited medications section below.

Continuous treatment with a GnRHa or surgical castration is mandatory for all patients in order to maintain castrate concentrations of testosterone (<50 ng/dL). The choice of GnRHa is at the discretion of the investigator. Dose and dose schedule (without interruption) will be consistent with the prescribing information and should only be adjusted if clinically indicated to maintain castrate concentrations of testosterone.

Salvage radiation for loco-regional pelvic disease and surgical procedures (eg, transurethral resection of the prostate [TURP], urethral and ureteral stent placement) to treat localized progression or symptoms are allowed. Patients receiving these therapies may continue on study drug .

### 6.1 PROHIBITED MEDICATIONS AND TREATMENTS

As a class effect, androgen receptor antagonists have been associated with seizures due to an off-target mechanism of action (GABAA inhibition). In preclinical studies, at very high doses, dogs treated with apalutamide had tremors and generalized seizures. Patients will be closely monitored for seizures, but as a precautionary measure, drugs known to decrease the seizure threshold and/or cause seizure will be prohibited while on study. A list of these medications can be found in [Appendix 5](#).

### 6.2 RESTRICTED THERAPIES

Investigators should refer to the apalutamide Investigator's Brochure (Sections 4.3.3.3 and 5.10) and associated addenda for complete details on the drug interaction potential of apalutamide. Highlights of drug interaction are summarized below.

- Strong CYP3A4 inducers: the potential for drug-drug interactions with apalutamide has not been tested clinically. Strong inducers of CYP3A4 (eg, phenytoin, carbamazepine, rifampin, rifabutin, rifapentine, phenobarbital, efavirenz, tipranavir, St. John's wort) should be avoided as much as possible. Additional information is provided in [Appendix 5](#).
- Apalutamide may also induce CYP3A4; therefore, caution should be taken when administered in conjunction with CYP3A4 substrates that have a narrow therapeutic index
- Strong CYP2C8 inhibitors (eg, gemfibrozil) should be used with caution with apalutamide
  
- The potential for drug-drug interaction between apalutamide and warfarin (e.g., Coumadin) is unknown at present. If a patient is taking warfarin, re-assess (prothrombin) PT/(international normalized ratio) INR as clinically indicated and adjust the dose of warfarin accordingly.
- Corticosteroids (Oral, IV, or IM): due to possible resistance mechanisms, which may be contributed by glucocorticoid receptor signaling, concurrent use of corticosteroids during the study is not recommended; short term use ( $\leq 4$  weeks) will be allowed if clinically indicated, however, its use must be tapered off as soon as possible.

### 6.3 LIFE STYLE GUIDELINES

To avoid risk of drug exposure through the ejaculate (even men with vasectomies), patients must use a condom during sexual activity while on study drug and for 3 months following the last dose of study drug. Donation of sperm is not allowed during the study and for 3 months following the last dose of study drug.

There are no data on the use of apalutamide in pregnancy. Maternal use of an anti-androgen is expected to produce changes in hormone levels that may affect fetal development. It is not known if apalutamide or its metabolites are present in semen.

If the patient is engaged in sexual activity with a woman of childbearing potential, a condom is required along with another effective contraceptive method consistent with local regulations regarding the use of birth control methods for patients participating in clinical studies and their partners. Highly effective forms of contraception include:

- established use of oral, injected or implanted hormonal methods of contraception; placement of an intrauterine device (IUD) or intrauterine (IUS) system;
- barrier methods: condom with spermicidal foam/gel/film/cream/suppository or occlusive cap (diaphragm or cervical/vault caps) with spermicidal foam/gel/film/cream/suppository;
- vasectomy;

- true abstinence (an option when this is in line with the preferred and usual lifestyle of the patient).

Two highly effective forms of contraception are required during the study and for 3 months after the last dose of study drug.

## **7. STUDY PROCEDURES AND GUIDELINES**

A Schedule of Activities representing the required testing procedures to be performed during the study is diagrammed in [Appendix 1](#).

Prior to conducting any study-related activities, written informed consent and any other authorizations must be signed and dated by the patient or patient's legal representative.

Every effort should be made to ensure that the protocol required tests and procedures are completed as described. However, it is anticipated that from time to time there may be circumstances outside of the control of the Investigator that may make it unfeasible to perform the test. In those cases, the Investigator should take all steps necessary to ensure the safety and wellbeing of the patient. When a protocol required test cannot be performed, the Investigator will document the reason for this and any corrective and preventive actions which he/she has taken to ensure that normal processes are adhered to as soon as possible. The study team should be informed of these incidents in a timely fashion.

### **7.1 CLINICAL ASSESSMENTS**

#### **7.1.1 Demographics**

Demographic information (e.g., date of birth, gender, race) will be recorded at Screening, as allowed per local country privacy law regulations.

#### **7.1.2 Medical History**

Relevant medical history, including history of current disease, other pertinent clinical conditions, and information regarding underlying diseases will be recorded at Screening.

#### **7.1.3 Physical Examination**

A complete physical examination will be performed by either the Investigator or a sub-Investigator at Screening. Qualified staff (e.g., nurses or physician assistants) may complete either a full or abbreviated physical exam at all other visits. New abnormal physical exam findings must be documented and followed by a physician or other qualified staff at the next scheduled visit.

The complete physical examination should include, but not limited to, general appearance, skin, neck, eyes, ears, nose, throat, breast, lungs, heart, abdomen, back, lymph nodes, extremities, and nervous system, as well as examination of known and suspected sites of disease. Height will be recorded at Screening only. Body weight will be recorded at Screening and every scheduled visit during treatment and at the end of treatment.

#### **7.1.4 Vital Signs**

Body temperature, blood pressure, pulse and respiratory rate will be performed after resting for 5 minutes at Screening and every scheduled visit during treatment and at the end of treatment.

### 7.1.5 Performance Status

The Eastern Cooperative Oncology Group (ECOG) performance status scale will be used ([Appendix 3](#)) and will be assessed at Screening and every subsequent clinic visit.

### 7.1.6 Adverse Events

Assessment of adverse events will include type, incidence, severity (graded by the National Cancer Institute [NCI] Common Terminology Criteria for Adverse Events [CTCAE], Version 4.0), timing, seriousness, and relatedness ([Appendix 4](#)). Adverse events will be assessed at every clinic visit.

### 7.1.7 Concomitant Medications/Therapies

All concomitant medication and concurrent therapies will be documented from the first dose of study drug until 28 days after the last dose of study drug. Name, indication for administration, and dates of medication or therapy will be captured.

### 7.1.8 Tumor Assessments

Disease assessments are to be performed as scheduled according to the calendar, regardless of treatment delays resulting from toxicity. Care must be taken in scheduling disease assessments to prevent the introduction of bias based on treatment delays.

Disease assessments will be performed at baseline (Screening), at 16-week intervals from Cycle 1 Day 1, whenever disease progression is suspected, and at the end of treatment. Imaging studies will include a CT scan of the chest, abdomen, and pelvis, plus a bone scan. At Screening, there will be an additional CT of the brain to rule out the presence of CNS metastases.

Radiographic confirmation of disease progression (appearance of distant metastasis) will be based on RECIST 1.1 and assessed by blinded independent central review (see below). For new bone lesions detected on bone scans, a second imaging modality (e.g., CT or MRI) will be required to confirm progression.

The same method of assessment and the same technique should be used at Screening and during follow-up. Intravenous (IV) contrast is required when not medically contraindicated. Patients who have a contraindication to IV contrast may have MRI exams of the brain, abdomen and pelvis performed in lieu of CTs and a non-contrast CT of the chest. Tumor evaluation by positron emission tomography (PET) scan or by ultrasound may not substitute for CT or MRI scans, but the CT portion of a PET/CT may be submitted in lieu of a dedicated CT. Additional requirements are provided in the Imaging Site Manual.

#### 7.1.8.1 Blinded Independent Central Review (BICR)

All scans will be submitted to a third-party core imaging laboratory for independent review of patient eligibility (within 3 days of receipt of imaging scans that pass quality assessment) and disease progression during the study according to an Independent Review Charter to be prepared by the core imaging laboratory in consultation with the Sponsor.

It is important to the integrity of the study that all imaging studies and pertinent clinical information (e.g., bone trauma, fracture, or infection) are forwarded to the core imaging laboratory throughout the study.

Further details regarding materials to be forwarded for central review can be found in the Imaging Manual and/or Investigator Site File.

## **7.2 CLINICAL LABORATORY MEASUREMENTS**

Blood will be obtained at the time points described in the Schedule of Activities and sent to a central lab for hematology and blood chemistry profile. [Appendix 2](#) lists all of the specific tests that will be performed. Complete details with regards to sample collection and shipment processes can be found in the Laboratory Manual and/or Investigator Site File.

Investigators may have additional blood tests performed for the purpose of planning treatment administration, dose modification, or following adverse events.

### **7.2.1 PSA**

Optional prescreening PSA evaluations will be performed by local laboratories.

All other PSA evaluations will be performed at the central laboratory. Results during treatment (until the time of the primary analysis) will be kept blinded to the patients, the Investigators, and the Sponsor, in order to preserve the double-blind nature of this study.

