Apalutamide or matched placebo will be administered orally on a continuous daily dosing schedule at a starting dose of 240 mg per day, the recommended Phase II dose selected based on preclinical projections of the optimal biological dose combined with safety and the PK/pharmacodynamic profiles observed during Phase I. Apalutamide or matched placebo will be given with continuous GnRH $\alpha$  (if patient has not been surgically castrated).

Patients will be followed for safety and efficacy as per the schedule of activities and will remain on study treatment until documented radiographic progression (development of distant metastases as assessed by blinded independent central review [BICR]) or the development of unacceptable toxicity. Treatment decisions will not be based on PSA as the clinical significance of PSA changes during treatment in the setting of NM-CRPC is unknown; therefore, PSA will be collected and analyzed by a central laboratory but

Investigators, patients, and the Sponsor will be blinded to the results until the time of the primary analysis.

Patients discontinuing treatment due to documented radiographic progression will enter the Long-term Follow-up Phase (See Section 8.9 and Appendix 1). Patients discontinuing treatment prior to documented radiographic progression will also enter the Long-term Follow-up Phase where they will continue to have scheduled disease assessments every 16 weeks until documented radiographic progression.

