### 5.2 BLINDING

Due to the objectives of the study, the identity of test and control treatments will not be known to investigators, research staff, or patients.

Only selected individuals not affiliated with the protocol will be unblinded to individual patient treatment assignment during the trial for the purposes of efficacy analyses and safety review. The randomization codes and all data sets will be stored in a secure area accessible only to these individuals, and only released on completion of the study and after the study database has been locked.

In emergency situations for reasons of patient safety (e.g., a serious unexpected/unlisted drug-related event; a medical emergency; a potentially life-threatening drug interaction), the blinding code may need to be broken. In those cases, whenever possible, a request for unblinding should be discussed with the Sponsor (or designee) prior to unblinding. Detailed instructions on the method for breaking the blind will be provided during site training and in the Investigator Site File.

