8.	Study Drug Compliance: Apalutamide and placebo bottle(s) including any unused tablets/capsules will be returned at the beginning of every cycle starting at Cycle 2 Day 1 and at end of treatment for drug accountability.
9.	Samples for Hematology, Blood Chemistry: All laboratory assessments will be performed by a central laboratory. PSA results will be kept blinded until the analysis of the primary endpoint. On Cycle 1 Day 1 only, clinical laboratory tests do not need to be repeated if the Screening tests were done within 4 days of Cycle 1 Day 1. Sites may perform additional local hematology and/or blood chemistry assays for the purposes of planning treatment administration, dose modification, or monitoring adverse events.
10.	Samples for PSA: Optional prescreening PSA evaluations will be performed by local laboratories. All other PSA valuations will be collected by the central laboratory; patients and investigators will be kept blinded until the analysis of the primary endpoint. On Cycle 1 Day 1 only, the PSA evaluation does not need to be repeated if the Screening tests were done within 4 days of Cycle 1 Day 1. For all subjects, at the time of unblinding and crossover, PSA data submitted to the central laboratory will no longer be blinded.
11.	Samples for TSH, fasting lipid panel, and testosterone: All laboratory assessments will be performed by a central laboratory every 16 weeks ( $\pm$ 2 days) from Cycle 1 Day 1. On Cycle 1 Day 1 only, clinical laboratory tests do not need to be repeated if the Screening tests were done within 4 days of Cycle 1 Day 1. Sites may perform additional local assays for the purposes of planning treatment administration, dose modification, or monitoring adverse events. See Appendix 2 for details on additional testing if TSH is abnormal.
12.	Brain Imaging: CT (or MRI, if use of contrast agent is contraindicated) scan of the brain will be performed at Screening and submitted for BICR to confirm patient eligibility (absence of brain metastasis).

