**APPENDIX 10: CROSSOVER TO OPEN LABEL APALUTAMIDE AFTER STUDY UNBLINDING**

At the time the decision is made to unblind the study, investigators will be notified by the sponsor. Subjects randomized to placebo who are currently on study treatment will be offered treatment with open-label apalutamide at 240 mg/day.

Subjects previously randomized to apalutamide will continue on protocol and follow the current schedule of activities (Appendix 1, with modifications below) and will be given open-label apalutamide.

For subjects who crossover from placebo to apalutamide, radiographic scans will no longer be required for the study and submitted for blinded central independent review. Subjects will be followed for progression per Investigator decision including symptoms, radiographic scans or PSA. PSA data submitted to the central laboratory will no longer be blinded. In addition, for all subjects, PK samples will no longer need to be collected at the time of unblinding.

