Assuming that the primary test for MFS is significant at alpha=0.05, TTM will then be tested at alpha=0.05. If significant, then PFS will be tested at alpha=0.05. If PFS is significant, then the Sponsor will perform the IA for SymProg. Assuming HR=0.75 for SymProg, then 427 events are required to yield 80% power at alpha=0.05. Suppose that *X1* events will have accumulated at the IA for SymProg, the information fraction would be t=X1/427. Efficacy of SymProg will be concluded if the stratified log-rank test statistic exceeds the critical value derived from the OBF-type alpha spending function.

The SymProg events re-estimation will be based on a conditional power of 90% for the next stage, calculated using the observed HR. Note that because of the variability associated with the observed HR, a conditional power of 90% is used in order to maintain an overall power of approximately 80% if the true HR is 0.75. The recommended number of SymProg events for the FA should be in the range of 191 (additional 191-XI events set as the minimum required for the next stage) to XI+(427-XI)*1.1 (not more than 10% increase on the preplanned number of events for the next stage). Because the true HR for SymProg is unknown, the minimum number of 191 is chosen to yield at least 80% power to detect an HR of 0.65 at an alpha level of 0.05.

The SymProg events re-estimation will be performed by the independent statistician who supports the IDMC activities. The dissemination and review of the specific results of the IA will be limited to the IDMC.

In order to maintain a strong control of the type I error rate for the SymProg analysis, an inverse normal p-value combination method will be used as the final test.⁷ The inverse normal p-value combination method allows flexible adaptations at an IA and creates a valid test that controls the type I error rate in a strong sense analytically. In this proposed design the adaptation is the potential adjustment of the required number of events for the next stage.

The final test statistics for the null hypothesis H₀: HR for SymProg ≥ 1 is defined as

$$Z = w_1 F^{-1} (1 - p_1) + w_2 F^{-1} (1 - p_2),$$

where $F^{-1}(x)$ is the inverse of the standard normal cumulative distribution function, $w_1 = \sqrt{t}$, $w_2 = \sqrt{1-t}$, p_1 denotes the first stage p-value and p_2 denotes the second stage p-value.

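### The protocol sets two unreconciled ends to the PSA mask, and one could release PSA to sites while the study is still blinded and later secondary endpoints are accruing

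*Protocol*

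**What the plan says.** **Release at the primary analysis.** Protocol 7.2.1 states: "Results during treatment (until the time of the primary analysis) will be kept blinded to the patients, the Investigators, and the Sponsor". It gives the protection of the double blind as the reason. Section 3.1 has the same end point: "Investigators, patients, and the Sponsor will be blinded to the results until the time of the primary analysis". Appendix 1, Footnote 9 reads: "PSA results will be kept blinded until the analysis of the primary endpoint". The first part of Footnote 10 says the same for patients and investigators. None of these attaches a condition about the result or about unblinding.

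**Release at unblinding.** Footnote 10 then closes with a different trigger: "For all subjects, at the time of unblinding and crossover, PSA data submitted to the central laboratory will no longer be blinded". Appendix 10 likewise says "PSA data submitted to the central laboratory will no longer be blinded", in text that starts from a sponsor decision: "At the time the decision is made to unblind the study, investigators will be notified by the sponsor". Section 3.1.1 makes crossover depend on unblinding together with a positive result. Section 8.10 refers to unblinding as something that may or may not happen. Section 5.2 holds the randomization codes, which are "only released on completion of the study and after the study database has been locked".

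**What continues after the primary analysis.** Under Protocol 13.2.2 and SAP 7.5.3, TTM and PFS have their final analyses with MFS. Symptomatic progression, OS and start of chemotherapy have only interim analyses then. On the symptomatic-progression interim, SAP 7.5.3 says: "The dissemination and review of the specific results of the IA will be limited to the IDMC". SAP Appendix 1 sets out the later analyses of all three endpoints.

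**The concern.** The primary analysis and the unblinding decision are different events, and the protocol does not say that one follows at once from the other. A central laboratory reading Footnote 10 finds both triggers in one paragraph and cannot tell which to apply.

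If it applies the earlier trigger, sites can receive PSA results while treatment allocation is still meant to be concealed. In this population PSA response is strongly related to arm. Time to symptomatic progression counts events that include surgery, radiation or new systemic therapy. Time to chemotherapy is a treatment decision in itself. A site that can infer the arm could make those decisions differently in the two groups. OS is exposed only indirectly, through later therapy.

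**Working it through.** **1. The plan's own figures.** The required number of events is d = (z_α/2 + z_β)² / [p(1−p)(ln HR)²], with p = 2/3, so p(1−p) = 2/9.

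- MFS, HR 0.70, 90% power: 10.507 / (0.2222 × 0.12722) = 371.7, so 372 events. This matches Protocol 13.6.
- Symptomatic progression, HR 0.75, 80% power: 7.849 / (0.2222 × 0.08276) = 426.8, so 427. This matches SAP 7.5.3.
- Minimum for symptomatic progression, HR 0.65, 80% power: 7.849 / (0.2222 × 0.18557) = 190.3, so 191. This matches SAP 7.5.3.

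The trigger in 7.2.1 is therefore the analysis at about 372 MFS events. Symptomatic progression has a separate event target, and SAP 7.5.3 leaves its count at that point unspecified. Protocol 15.6 foresees follow-up to about 9 months after last patient in for MFS and about 41 months for OS. That is 41 − 9 = 32 months of planned follow-up after the primary analysis.

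**2. The two triggers side by side.**

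| Place | End of the PSA mask | Condition |
|---|---|---|
| Protocol 3.1, 7.2.1 | Primary analysis | None |
| Appendix 1, Footnote 9 | Primary-endpoint analysis | None |
| Appendix 1, Footnote 10, first part | Primary-endpoint analysis | None |
| Appendix 1, Footnote 10, last sentence | Unblinding and crossover | Study unblinded |
| Appendix 10 | Study unblinding | Sponsor decision |

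**3. When the difference matters.**

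- *MFS, TTM or PFS not significant:* the hierarchy in SAP 7.5.3 stops. No later endpoint can be claimed, so no confirmatory conclusion is biased.
- *All endpoints significant at the first analysis:* SAP Appendix 1 stops the study. Nothing remains to be biased.
- *Positive and unblinded at once:* arms are known and placebo men are offered apalutamide. PSA adds nothing.
- *MFS, TTM and PFS significant, later endpoints open, study still blinded (or unblinding not yet decided):* the first trigger releases PSA and the second does not. This is the exposed case.

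**4. How much PSA tells about the arm.** Inputs:

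- 2:1 allocation, so the prior for apalutamide is 2/3 (Protocol 3.1).
- 12-week response on apalutamide of 0.91 (Protocol 1.1.3, NM-CRPC group).
- Response on placebo, q, which the documents do not give. I assume 0 to 0.20. Men enter with rising PSA (inclusion criterion 2.1), so low values are plausible.

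The rule is to call responders apalutamide and non-responders placebo.

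- Correct overall = (2/3)(0.91) + (1/3)(1 − q)
- P(apalutamide | response) = (2/3)(0.91) / [(2/3)(0.91) + q/3]
- P(placebo | no response) = (1/3)(1 − q) / [(1/3)(1 − q) + (2/3)(0.09)]

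| q | Correct overall | P(apalutamide given response) | P(placebo given no response) |
|---|---|---|---|
| 0 | 94.0% | 100% | 84.7% |
| 0.02 | 93.3% | 98.9% | 84.5% |
| 0.10 | 90.7% | 94.8% | 83.3% |
| 0.20 | 87.3% | 90.1% | 81.6% |

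For example, at q = 0.20: 0.6067 + 0.2667 = 0.873. Guessing apalutamide for every man is right in 66.7%, so PSA response adds 20.7 to 27.3 percentage points.

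**5. Who is exposed.** Appendix 1 schedules PSA during treatment and at the end of treatment, and none in long-term follow-up. New results after the primary analysis therefore come from men still on treatment or just stopping it.

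**The case against.** The strongest reply is that the texts can be read together. Sections 3.1 and 7.2.1 say only how long results are masked at a minimum, while Footnote 10 and Appendix 10 say when release happens. No section tells the laboratory to send results to sites at 372 events. There is also a benign reason for the earlier date: SAP 7.7.2 analyses PSA at the primary analysis, so someone must see the data then. Section 3.1 says that treatment decisions will not rest on PSA, and Section 10 says not on PSA alone. Some symptomatic-progression events, such as pathologic fracture and cord compression, are not investigator choices.

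Much of this stands and limits the size of the point. It does not remove it. A plain reading of an until clause is that masking then ends, and Footnote 10 carries both triggers. The SAP 7.7.2 analyses need release to analysts, not to sites. The safeguards address acting on a PSA value, not knowing the arm.

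Two stronger readings are tempting, and the documents support neither. A reader might infer that PSA reveals the arm of every man. On the Phase II figure about 9% of apalutamide men would not respond, and a judgement needs a change from baseline rather than a single value. A reader might also count every later symptomatic-progression event as exposed. The number at the interim is not given, men off treatment have no further scheduled PSA, and events after formal unblinding are not affected by a PSA leak.

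**Conclusion.** The conflict is real and is in the current text. Following 7.2.1 literally can defeat the purpose that 7.2.1 itself states. The consequence is conditional. It arises only if MFS, TTM and PFS are significant with later endpoints still open while the study stays blinded, or in the gap before an unblinding decision. The documents give no length for that gap.

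Within that window PSA response would identify the arm in about 87-94% of men with a baseline and a week-12 value, against 67% without it. This rests on the Phase II response of 91%, from an NM-CRPC group of 51, carrying over to this trial, and on an assumed placebo response of 0-20%. The bias in the hazard ratios for symptomatic progression or chemotherapy cannot be calculated from the documents. The point should be corrected because the remedy costs almost nothing. It does not call the MFS analysis, the event targets or the type I error control into question.

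**What to change.** State one rule in Protocol 3.1, 7.2.1 and Appendix 1 Footnotes 9 and 10: PSA results stay masked to patients, investigators and the Sponsor's blinded study team until the formal unblinding decision described in Appendix 10. Add that at the primary analysis PSA is released only to the unblinded analysis team, for the PSA analyses in SAP 7.7.2. The Sponsor should be named explicitly, because 3.1 and 7.2.1 mask it while Footnote 10 mentions only patients and investigators.

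The cost is a few aligned sentences and an instruction to the central laboratory. No data collection, sample size, power or alpha changes.
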